6.5.7.7. Pregnancy Reporting

If a female patient becomes pregnant during the study through 90 days following the last dose of study drug, or through their last visit in the study (whichever is later), the Investigator must report the pregnancy to the Sponsor or designee within 24 hours of being notified of the pregnancy. Details of the pregnancy will be recorded on the pregnancy reporting form. The patient should receive any necessary counseling regarding the risks of continuing the pregnancy, the possible effects on the fetus, and be counseled to not breastfeed for 90 days after the last dose of study drug.

The pregnancy should be followed by the Investigator until completion. At the completion of the pregnancy, the Investigator will document the outcome of the pregnancy. If the outcome of the pregnancy results in a postpartum complication, spontaneous abortion, stillbirth, neonatal death,

or congenital anomaly, then the Investigator should follow the procedures for reporting an SAE as outlined in Section 6.5.7.4.

6.5.7.8. Overdose Reporting

An overdose is defined as any dose administered to or taken by a patient (accidentally or intentionally) that exceeds the highest daily dose, or is at a higher frequency, than included in the protocol. When an overdose is suspected, the Investigator should inform the Medical Monitor.

6.5.8. COVID-19 Data Collection

Information on the COVID-19 infection status of the patient, if known, and other information on the impact of the COVID-19 pandemic on the patient's participation in the study will be collected.

6.6. Biomarkers, DNA Genotyping, and Biospecimen Repository

Alnylam's RNAi therapeutics platform permits the highly specific targeting of investigational therapies based on genetic sequence. It is possible that variations in the target genetic sequence will result in variations in drug effect.

More generally, genetic variations may account for the well-described heterogeneous manifestations of disease in patients with hATTR amyloidosis, as well as their responses to treatment.

Where allowed per local regulations, ethics committee (IRB/EC) approval, and patient consent (and assent, where applicable), samples will be collected as part of this study to permit exploratory investigations and the application of novel approaches to bioanalyses that may further elucidate the outcomes of this study, or potentially advance understanding of the safety, mechanism of action, and/or efficacy of ALN-TTRSC02 and patisiran.

Biological specimens will be collected at the intervals indicated in the Schedule of Assessments (Table 1 through Table 6). Potential exploratory investigations may include DNA, RNA, or biochemical metabolite assessments as they relate to disease progression, efficacy or safety.

The biospecimen repository will also include residual material from routine samples (safety laboratory samples, PK samples, etc.) that are obtained during the study.

These specimens will be securely stored in a central biorepository for up to 10 years following the completion of this clinical study (ie, last patient last visit), or as per local regulations. After 10 years have elapsed, samples will be destroyed.

Details regarding the collection, processing, storage, and shipping of the samples will be provided in the Laboratory Manual.

Exploratory analysis of these biospecimens will be performed by Alnylam Pharmaceuticals or its designees.

When biobanking is permitted by local regulation, study participants will be advised during the informed consent process of these biobanking details and the potential for exploratory investigation of their samples.

6.7. Pharmacoeconomic Assessments

6.7.1. Patient and Caregiver Impact Survey

To complement medical records, information about how hATTR amyloidosis impacts the lives of patients and their caregivers will be collected at the timepoints specified in the Schedule of Assessments (Table 1 to Table 4). The Patient and Caregiver Impact Survey includes questions related to how hATTR amyloidosis affects patients, including their symptoms at the time of diagnosis, utilization of various healthcare providers, employment status, and need for government compensation/assistance. Questions will also be asked about how hATTR amyloidosis impacts the employment status of the patient's caregiver and patients' need for both informal and professional caregivers.

6.7.2. Hospitalization, Urgent Healthcare Visits, Surgeries, and Procedures

[figure not shown]
Hospitalization, urgent healthcare visits, surgeries, and procedure information will be collected on a separate eCRF for pharmacoeconomic evaluations, as specified in the Schedule of Assessments (Table 1 to Table 4). As described in the beginning Section 6, in situations where a study visit is unable to be completed at the study center, the study physician (or delegate) may verbally contact the patient within the expected study visit window to assess hospitalizations, urgent healthcare visits, surgeries, and procedures.

Prior hospitalization, urgent healthcare visits, surgeries, and procedure information through 12 months prior to first dose should be collected at Screening.

6.7.3. Patient Experience Survey

The Patient Experience Survey will be administered to understand patients' level of satisfaction with their current hATTR amyloidosis therapy and their level of comfort using this therapy. This survey will be administered at the timepoints specified in the Schedule of Assessments (Table 1, Table 2, and Table 4).

6.7.4. Patient Preference Survey

 The survey aims to understand patients' preferred method of treatment administration and the primary reasons for their preference. This survey will be administered at the timepoints specified in the Schedule of Assessments (Table 4).

7. STATISTICS

The principal features of the planned analysis are presented in this section. A separate SAP will be finalized prior to first patient dosed. The SAP will detail the implementation of the statistical analyses in accordance with the principal features stated in the protocol.

7.1. Determination of Sample Size

Approximately 160 patients will be enrolled in this study, with a 3:1 randomization ratio to either ALN-TTRSC02 or patisiran.

The sample size was chosen to enable an adequate characterization of the long-term safety profile, as well as the efficacy of ALN-TTRSC02 in this patient population. For the primary efficacy endpoint of mNIS+7 and the key secondary endpoint of Norfolk QoL-DN total scores, the ALN-TTRSC02 arm in the Phase 3 study will be compared to the placebo arm from the APOLLO study. For the mNIS+7 change from baseline at 9 months, the observed mean (\pm standard deviation [SD]) was 15 ± 17 points for the placebo arm from the APOLLO study. Assuming a mean change of 0 points for the ALN-TTRSC02 arm, there is $>90\%$ power to establish the superiority over placebo using a 2-sided t-test with a significance level of 0.05. For the Norfolk-QoL DN total score change from baseline at 9 months, the observed mean (\pm SD) was 11.5 ± 19.2 points for the placebo arm from the APOLLO study. Assuming a mean change of -4 points for the ALN-TTRSC02 arm, there is $>90\%$ power to establish the superiority over placebo using a 2-sided t-test with a significance level of 0.05.

For safety, a sample size of >100 patients on ALN-TTRSC02 can provide reasonable assurance that the true cumulative one-year incidence of adverse drug events (ADE) is no greater than 3% when no ADE is observed.

To match the cardiac disease severity with the APOLLO study population, the study plans to enroll no more than 15% of patients with NT-proBNP values greater than 3000 ng/L.

7.2. Statistical Methodology

Additional data summaries to help understand any impact of the COVID-19 pandemic and any descriptive comparison of [REDACTED] on efficacy, PD and safety assessments will be outlined in the SAP.

7.2.1. Populations to be Analyzed

The population analysis sets are defined as follows:

- Modified ITT (mITT) population: All randomized patients who received any amount of study drug. Patients will be grouped by their randomized treatment group.
- TTR Per-protocol (PP) Population: All mITT population patients with a nonmissing TTR assessment at baseline and ≥ 1 trough TTR assessment associated with adequate treatment compliance between Month 6 and Month 18. Specific details will be provided in the SAP.
- Safety Population: All randomized patients who received any amount of study drug, grouped according to the treatment actually received.
- PK Population: All randomized patients who received any amount of study drug and have at least 1 post dose blood sample for PK parameters and have evaluable PK data.
- Patients with cardiac involvement: All patients in the mITT population who had pre-existing evidence of cardiac amyloid involvement. Specific details will be provided in the SAP.

The primary population for efficacy analysis will be the mITT population, except TTR percent reduction analysis, which will be conducted in the TTR PP population. Safety analysis will be conducted in the safety population. PK analysis will be conducted in the PK population. Selected endpoints will be analyzed in the cardiac subpopulation.

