7.2.5. Efficacy Analyses

This Phase 3 study will use the placebo arm of the APOLLO study as an external control. Patient-level data from this study will be compared with patient-level data from APOLLO for efficacy analyses. For the primary and secondary clinical efficacy endpoints, the ALN-TTRSC02 arm in this study will be compared to the placebo arm from the APOLLO study. For the secondary endpoint of TTR percent reduction, the ALN-TTRSC02 arm in this study will be compared to the patisiran arm in this study. The treatment comparison will be conducted at Month 9 and/or Month 18. The efficacy endpoints beyond 18 months will be summarized descriptively.

The patisiran arm in this study will mainly serve as a reference arm. For the clinical efficacy endpoints at Month 9 and Month 18, the patisiran arm will be summarized descriptively and the treatment difference between ALN-TTRSC02 and patisiran arm in this study will not be tested.

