7.2.5.2. Secondary Endpoints

For the secondary clinical efficacy endpoints, the treatment comparison will be made between the ALN-TTRSC02 group in this study and the placebo group in the APOLLO study at Month 9 or Month 18 as specified. For the TTR percent reduction endpoint, the ALN-TTRSC02 group will be compared with the patisiran group in this study. To control the overall type I error, the secondary endpoints will be tested in the following hierarchical order:

- Norfolk QoL-DN total score change from baseline at Month 9
- 10-MWT gait speed change from baseline at Month 9
- mNIS+7 change from baseline at Month 18
- Norfolk QoL-DN total score change from baseline at Month 18
- 10-MWT gait speed change from baseline at Month 18
- mBMI (BMI [kg/m²] multiplied by serum albumin level [g/L]) change from baseline at Month 18
- R-ODS change from baseline at Month 18
- TTR percent reduction through 18 months

For change in Norfolk QoL-DN total score and 10-MWT gait speed from baseline at Month 9, the analysis will be based on an ANCOVA model similar to the model described for the analysis of change in mNIS+7 from baseline at Month 9, while adjusting for baseline value of the endpoint being modeled and including baseline NIS score (<50 vs ≥50) as an additional factor in the model. For these 2 endpoints, data that are missing will be multiply imputed separately for each treatment group using a regression procedure based on baseline covariates. The details will be specified in the SAP.

For change from baseline at Month 18 analyses, the analysis will be based on a mixed-effects model for repeated measures (MMRM), adjusting for a covariate (baseline value for the endpoint being modeled), categorical factors (treatment group, visit [Month 9 vs Month 18], genotype, age of disease onset, baseline NIS score), and an interaction term (treatment group by visit). For mNIS+7, baseline NIS score will not be included in the model.

In the APOLLO study, mBMI was not assessed at Month 9 or Month 18. The average values of Day 189 and Day 357 will be derived as Month 9, and the Day 546 value will be substituted as Month 18.

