The TTR percent reduction through Month 18 will be derived as the average trough TTR percent reduction from Month 6 to 18 which is the steady state period for both ALN-TTRSC02 and patisiran. A Hodges-Lehmann method stratified by previous TTR stabilizer use (yes vs no) will be used to estimate the 95% CI for the median difference between the ALN-TTRSC02 and patisiran groups in this study. Non-inferiority will be declared if the lower limit of the 95% CI for the treatment difference is greater than -10%. A sensitivity analysis will be conducted to compare the TTR percent reduction between the ALN-TTRSC02 group from this study and the pooled patisiran groups from this Phase 3 study and the APOLLO study.

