This change has been made as part of the overall strategy of reducing visits and assessments during the COVID-19 pandemic. Removal of these assessments is not expected to have a meaningful impact on the TTR efficacy endpoint at Month 18 as our modeling data support that there are minimal fluctuations in TTR levels over the dosing interval following Week 12; ie, following 2nd dose of ALN-TTRSC02.

- **Timing of other assessments**

Reduced the frequency of select assessments or combined assessments from different visits to align with dosing visits in order to limit the number of times a patient needs to visit the site/interact with home healthcare professionals and reduce potential exposure to COVID-19.

- **Secondary Endpoint of TTR percent reduction**

Changed the secondary endpoint related to comparison of TTR percent reduction in the ALN-TTRSC02 arm compared to patisiran through 9 months to 18 months.

This change is being implemented to address concerns with regard to missed doses related to COVID-19 during critical time periods preceding the Month 9 assessment with potential impact to the integrity of this endpoint. TTR percent reduction through Month 9 was planned to be evaluated for noninferiority compared to the within-study randomized patisiran arm. This endpoint was specified in the SAP to be evaluated on the Per-protocol (PP) Population. With dosing flexibility adopted due to the COVID-19 pandemic, it is expected that the number of patients qualifying for the PP Population will be substantially reduced, thus greatly reducing power for the originally planned Month 9 analysis of TTR percent reduction. Changing TTR percent reduction from Month 9 to Month 18 is anticipated to allow for a more viable noninferiority comparison with sufficient power.

- **Collection of Information Related to COVID-19**

Information related to the impact of the COVID-19 pandemic on patient participation in the study will be collected for each patient in order to enable analysis of the impact of the COVID-19 global pandemic on clinical trial data.

- **Updates to Study Administration Text**

Text was updated to provide clarification of Investigator responsibilities regarding communication of new study information to patients and IRB/IECs.

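### The only test between the randomised arms, TTR non-inferiority, is assigned to a compliance-selected per-protocol set with no mITT analysis named beside it

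*Protocol*

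**What the plan says.** All references are to the current, amended protocol text.

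- **Population.** Section 7.2.1 uses mITT for efficacy, "except TTR percent reduction analysis, which will be conducted in the TTR PP population". A patient enters that set with a baseline TTR value and "≥ 1 trough TTR assessment associated with adequate treatment compliance between Month 6 and Month 18". On the compliance rule it adds: "Specific details will be provided in the SAP".
- **Comparison.** Section 7.2.5.2: "For the TTR percent reduction endpoint, the ALN-TTRSC02 group will be compared with the patisiran group in this study". For the clinical endpoints, Section 7.2.5 says that "the treatment difference between ALN-TTRSC02 and patisiran arm in this study will not be tested". TTR is thus the only hypothesis test between randomised groups. It stands last in the hierarchy.
- **Criterion.** Section 7.2.5.2: "Non-inferiority will be declared if the lower limit of the 95% CI for the treatment difference is greater than -10" percent, by a Hodges-Lehmann interval stratified by previous stabiliser use.
- **Sensitivity analysis.** Section 7.2.5.2 names one for TTR. It adds APOLLO patisiran patients to the within-study patisiran arm. Section 7.2.3 plans missing-data sensitivity analyses for mNIS+7 and Norfolk QoL-DN only.
- **Role.** Section 1.5 says that a similar (non-inferior) TTR reduction helps to justify using the APOLLO placebo arm as control.

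**The concern.** Compliance, and still being on drug at Month 6, are both decided after randomisation. A patient who stops before Month 6 has no qualifying trough and leaves the test. If patients leave for different reasons or at different rates in the two arms, the retained groups are no longer the groups that randomisation made comparable.

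The regimens make unequal selection plausible. Patisiran has far more dosing occasions and a much shorter allowance for a late dose. At stake is the one result in the trial that could rest on randomisation, and it is also offered as support for the external comparison that carries the primary endpoint and most of the secondary ones.

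**Working it through.** **1. Is there a figure to reproduce?** No. Section 7.1 gives power for mNIS+7 and Norfolk QoL-DN and a safety statement. It gives no SD, power or expected retention for TTR. Planned size is about 160 at 3:1, so 160 × 3/4 = 120 and 160 × 1/4 = 40.

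**2. Are the chances of being non-compliant alike?**

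| | ALN-TTRSC02 | Patisiran |
|---|---|---|
| Doses, Week 24 to Week 78 (Tables 1 and 2) | Weeks 24, 36, 48, 60, 72: 5 | every 3 weeks: (78 - 24)/3 + 1 = 19 |
| Late dose allowed (5.2.2.1, 5.2.2.2) | up to 8 weeks, or as the Medical Monitor decides | up to 7 days, for pandemic reasons, after consultation |
| Who may give it outside the clinic | healthcare professional; patient or caregiver under pandemic conditions | healthcare professional |

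The opportunities differ in number and in kind. A common compliance rule need not select alike in the two arms.

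**3. How far could selection move the comparison?** In one arm, let *f* be the share excluded and *g* the number of points by which their mean TTR reduction falls below that of the retained patients. Then

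mITT mean = (1 - f)R + f(R - g) = R - fg, so per-protocol mean minus mITT mean = fg.

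The treatment difference (ALN-TTRSC02 minus patisiran) moves by f_A·g_A - f_P·g_P. A positive value favours non-inferiority in the per-protocol set. All values of f and g below are assumptions.

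- *Balanced, late doses only.* f = 0.20 in each arm. Take g = 7 and 10 points, borrowing the Amendment 2 rationale's modelled effects of one delayed dose. Shift = 0.20 × 7 - 0.20 × 10 = 1.4 - 2.0 = -0.6 point, making the claim slightly harder. This is generous, because one late dose affects only part of a patient's Month 6 to 18 average.
- *One arm only, off treatment.* f = 0.10 with g = 80, meaning that nearly all the reduction is lost (APOLLO patisiran means in Section 1.4.1 are 82.6% and 84.3%). Shift in that arm's mean = 0.10 × 80 = 8 points. It favours the claim if the arm is ALN-TTRSC02 and opposes it if it is patisiran.

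**4. Allow for the estimator.** The plan uses a Hodges-Lehmann median difference, which resists outlying patients. In the second case 10% of pairwise differences lie far out, so the median falls at the 0.40/0.90 = 0.444 quantile of the rest. For normal data that is a shift of 0.140 × √2 × SD = 0.198 × SD: 2.0, 3.0 and 4.0 points for assumed SDs of 10, 15 and 20. In the first case the Hodges-Lehmann shift stays near 0.6.

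**5. Does the named sensitivity analysis help?** No. Pooling APOLLO patisiran patients changes the comparator and adds non-randomised patients. It does not restore those excluded for compliance.

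**The case against.** **Per-protocol is a respectable choice for non-inferiority.** Keeping non-adherent patients can pull the arms together, so dropping them can be the stricter course. That stands. The weakness is naming the per-protocol set alone, since neither set is reliably conservative here.

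**The filter is lenient.** One qualifying trough in twelve months is enough, and the set is a subset of mITT still compared by randomised arm. That also stands: randomisation is weakened, not lost.

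**The SAP may contain an mITT analysis.** It may, and the compliance threshold is properly left to it. But the population for this test is fixed in the protocol, and nothing there makes the claim depend on a second set.

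**The endpoint is last in the hierarchy.** It gates no other test, which limits the harm. Its supporting role in Section 1.5 remains.

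A reader might infer three stronger things that the documents do not support:

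- *That the sponsor expects the present set to shrink badly.* The Amendment 2 rationale does say that "it is expected that the number of patients qualifying for the PP Population will be substantially reduced", but about the Month 9 analysis that it replaced. Its next sentence expects sufficient power at Month 18. No retention figure is given for the current set.
- *That individual troughs after late doses are discarded.* Section 7.2.1 defines which patients enter, and Section 7.2.5.2 averages the troughs from Month 6 to 18. Neither states a sample-level exclusion.
- *That the modelled losses of 7% and about 10% nearly use up the margin.* They are effects of one delayed dose in one patient. The margin applies to a between-arm difference in patient averages.

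**Conclusion.** The point holds as a weakness of specification. The protocol's only randomised hypothesis test is run in a set selected on post-randomisation compliance, with regimens that can make selection differ by arm, and no mITT analysis is named beside it.

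Its size and direction cannot be determined from the document. The illustrations run from about 0.6 point to 8 points on an arm mean, or about 2 to 4 points on the planned estimator, against a margin of 10. The upper end rests on assumptions that nothing in the protocol confirms: exclusions in one arm only, near-complete loss of TTR reduction, normal data, and SDs of 10 to 20. The primary endpoint is not affected. The change should be made, but the trial's main conclusions do not hang on it.

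**What to change.** In Sections 7.2.1 and 7.2.5.2, add the same stratified Hodges-Lehmann analysis in mITT: all randomised, dosed patients with a baseline and any Month 6 to 18 TTR value, regardless of compliance. Include values from the modified efficacy visits after discontinuation, where Table 3 already schedules TTR. Claim non-inferiority only if the lower 95% limit exceeds -10% in both sets. Report the number and reasons for exclusion by arm.

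The cost is wording, one repeat analysis and a slightly harder claim. With 120 and 40 patients and no true difference, approximate power in mITT is Φ(10/SE - 1.96), where SE = SD × √(1/120 + 1/40) = 0.183 × SD. That gives over 99.9%, 95.5% and 78.2% for assumed SDs of 10, 15 and 20. Requiring both sets lowers these somewhat.

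One point needs stating with the change. Section 4.3.1 lets patients who stop study drug receive local standard treatment, so some later mITT values may reflect another therapy. The text should say that such values are used as observed.

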7.2.2. Examination of Subgroups

Subgroup analyses will be conducted for selected endpoints. Detailed methodology will be provided in the SAP.

